### 1.8.2 Clinical part

The patients will be allocated (1:1) to vitamin D + Ca-tablets  $\pm$  Jarlsberg cheese. All the participants will get new delivery of vitamin D and Ca-tablets every four weeks. The patients allocated to Jarlsberg will additionally receive Jarlsberg cheese. The patients will receive a compliance & activity form and asked to fill in every day. All the patients meet for new visits at week 4, week 16, and week 32. Patients allocated to only vitamin D + Ca tablets at baseline well additionally meet for visits at week 20 and week 48. At all these visits blood samples for

measurement of Osteocalcin, CTX-1, PINP, BALP and PTH will be drawn fasting in the morning, and concomitant medication and treatment compliance recorded. The main visits will be performed every 16 weeks. New DXA screening will be performed. Patients obtaining a BMD T-score  $\leq -2.5$  will discontinue the study and switched to antiresorptive treatment plus daily OED of Jarlsberg cheese. The daily food intake during four consecutively days will be recorded on the Diet-App. Blood samples for measurements of Osteocalcin, CTX-1, PINP, BALB and PTH will be drawn fastening in the morning at every visits. Furthermore, blood samples for measuring and biochemical variables, HbA1C and Lipids, will be recorded. The CTCAE will be recorded as well. The visit at Week 32 and Week 48 will be the last observation in the study for the patients initially allocated to Jarlsberg and controls, respectively. In addition to the mentioned variables blood samples for measurement of Interleukins and Cytokines will be performed. All the patients completed the study will be offered to continue the daily intake of Jarlsberg cheese. These patients will be followed up one year after the last visit with a new DXA and a blood sampling for measurements of the Osteocalcin level and the bone markers PINP, CTX and BALP.

**1.9: Sample size:** With a significance level of 5%, a power of 90% and a Clinically Relevant Difference (CRD) of one time the Standard Deviation in change of BMD, at least 24 patients in each group must finalize the study. With an expected drop-out rate of 25%, 30 patients in each group must be included.

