#### 2.4: Aims.

- To estimate the effect of daily optimal efficacy dose (OED) of Jarlsberg cheese on BMD and bone markers to patients with Borderline Osteoporosis (BO).
- To compare daily intake of Calcium (Ca) and vitamin D with and without OED of Jarlsberg on BMD and bone markers to BO patients.
- To compare daily intake of Calcium (Ca) and vitamin D with and without OED of Jarlsberg on Time-to-Osteoporotic (TTO) treatment is recommended.

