#### 6.2.2: Comparative phase

All the participants meet for clinical investigations at week 4 and week 16 in the comparative phase of the study. At week 4, blood samples will be taken for measurements of Osteocalcin and the BTMs. Additionally, concomitant medication, adverse events (AE) and treatment compliance will be recorded. Cheese and vitamin D + Ca for the next 4 weeks will be delivered. A new delivery will be handed over by a representative from the Meddoc team at week 8 and week 12 in the study. The last clinical investigation in this comparative phase will be performed at week 16. The physical examination will be equal with the one performed in the screening phase. The patients must perform a new diet registration during the following 4 days and undergo the second DXA investigation for measurements of BMD. Additionally, the patients will record their change in concomitant medication. Blood samples will be collected for measurements of Osteocalcin, vitamin K2, BTMs, HbA1C, Lipids and other hematological and biochemical variables. Patients with a T-score < -2.5 based on the DXA investigation will be classified as Osteoporotic and withdrawn from the study. If possible and

in accordance with the responsible investigator, the patient will be given Antiresorptive treatment in addition to OED of Jarlsberg cheese and vitamin D + Ca.

The patients randomized to only vitamin D + Ca (Controls) at baseline will now receive OED of Jarlsberg cheese equal with the other patients and continue in the follow-up phase of the study. Cheese for the next 4 weeks will be delivered together with compliance & activity form.

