### **10.1: Discontinuation not related to the study question**

If patient discontinue the study of administrative reasons or reasons documented not related to the trial treatment will be classified as "Drop out" and replaced by new participant. The dropouts will be described specially in the statistical analysis.

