### **10.2: Discontinuation related to the study question**

If patient discontinue the study of reasons related or might be related to the trial treatment will be classified as "Withdrawal". These will not be replaced by new participants but included in both the Per-Protocol (PP) and the ITT analysis using the procedure "Last observations carried forward" (LOCF).

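### Patients withdrawn for a T-score below the limit leave on the main variable, yet section X never says whether they are replaced or kept in the analysis

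*Protocol*

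**What the plan says.** **Exit rule.** Protocol 6.2.2 (week 16) states: "Patients with a T-score < -2.5 based on the DXA investigation will be classified as Osteoporotic and withdrawn from the study". 6.2.3 repeats this for the later DXA visits, and 4.1 has the same rule. The synopsis (1.8.2) says that such patients "will discontinue the study and switched to antiresorptive treatment plus daily OED of Jarlsberg cheese", but sets the limit at -2.5 or lower, where the other three places have strictly below -2.5.

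**Aims.** Change in BMD is the main response variable (1.7). The third aim (1.3, 2.4) compares the arms "with and without OED of Jarlsberg on Time-to-Osteoporotic (TTO) treatment is recommended".

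**Exit classes.** Section X has two.
- 10.1: "If patient discontinue the study of administrative reasons or reasons documented not related to the trial treatment will be classified as" a drop-out, who is "replaced by new participant. The dropouts will be described specially in the statistical analysis".
- 10.2: "If patient discontinue the study of reasons related or might be related to the trial treatment will be classified as" a withdrawal, who is not replaced and enters both PP and ITT by LOCF.

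Neither class mentions the T-score rule, and 6.2.2 and 6.2.3 do not refer to section X.

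**Timing.** Controls switch to cheese at week 16 (4.1), so the randomised comparison ends at the visit where the first of these exits can occur.

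**The concern.** The exit is triggered by the outcome. The patients concerned have the lowest BMD, and if the cheese works most of them are controls. Section X asks a different question: whether the reason for leaving is related to trial treatment. Progression to an osteoporotic reading does not answer that. In a patient eating cheese it might be judged possibly related. In a control it could be recorded as the course of the disease, hence unrelated.

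4.1 calls the trial open (1.6.1 says single-blinded), so the judgement can be made with both arm and DXA result known. The two classes could then fill differently by arm. Replacement is decided during recruitment, and a later analysis plan cannot undo it. At stake are the size of the week-16 BMD difference, the third-aim event count and, under 10.2, the BMD course after week 16.

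**Working it through.** **1. The plan's own figures.** The plan gives no expected number of T-score exits. It gives 24 completers per group for a difference of 1 SD. With n = 2(z₀.₉₇₅ + z_power)²:
- 90% power (1.9): 2 × (1.960 + 1.282)² = 21.0, so 22.
- 95% power (11.3): 2 × (1.960 + 1.645)² = 26.0, so 26.

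The stated 24 lies between them and is not disputed here. What matters is the 0.09 g/cm2. Section 1.9 treats the 1 SD as an SD of change. Section 11.3 derives 0.09 from the spread of total BMD with a CV of 0.07, and 0.09 / 0.07 = 1.29 g/cm2 is a BMD level, not a change. The SD of a 16-week change may be much smaller, so a range of 0.02 to 0.09 is shown.

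**2. Week 16 under each class.** The DXA that triggers exit is itself the week-16 value.
- 10.2: LOCF has nothing to fill at week 16. The observed value is used and the event is on record.
- 10.1, with the patient replaced and left out: the low tail is cut off, mostly in controls.

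**3. Size if exits are removed.** Simulation. Assumptions not in the documents:
- 1 T-unit = 0.09 g/cm2
- baseline T ~ N(-1.3, 1)
- 30-80% of the variance of change is measurement noise
- true difference of 1 SD of change

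Entry is T between -2.5 and -1.0 (1.8.1) or between -2.5 and 0.0 (1.4, 3.2.1). Exit is a measured week-16 T < -2.5. The loss is the fall in the difference in mean change when exits are left out.

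| SD of change (g/cm2) | Entry limit | Exits, control v Jarlsberg | Loss |
|---|---|---|---|
| 0.09 | -1.0 | 18-21% v 3-4% | 22-25% |
| 0.09 | 0.0 | 12-14% v 2-3% | 14-17% |
| 0.045 | -1.0 | 9-10% v 1-2% | 10-11% |
| 0.045 | 0.0 | about 6% v 1% | about 6% |
| 0.02 | -1.0 | about 4% v 1% | about 4% |
| 0.02 | 0.0 | about 2% v under 1% | about 2% |

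**4. Same check on other assumptions.** Uniform baseline T, 1 T-unit = 0.10-0.12 g/cm2, ANCOVA on baseline, true difference 0.09, SD 0.09:
- Observed value kept, as under 10.2: 0.090 recovered.
- Exits removed: from 0.0897 to 0.0776 (1 - 0.0776/0.0897 = 14%) up to 0.0899 to 0.0658 (1 - 0.0658/0.0899 = 27%).
- Expected exits: 3.6-6.8 of 30 controls against 0.8-1.5 of 30 on cheese. Each is a candidate third-aim event.

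With SD 0.02-0.03 and differences of 0.01-0.09, the loss is 2-6%, with 0.8-2.4 exits among 30 controls.

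**5. Later visits under 10.2.** A control who exits at week 16 has a pre-cheese reading x₁₆ copied to weeks 32 and 48, which are 16 and 32 weeks on cheese. The on-cheese change is x₁₆ - x₁₆ = 0 by construction. On the exits in step 4, that is 3.6/30 to 6.8/30 = 12-23% of controls at SD 0.09, and 0.8/30 to 2.4/30 = 3-8% at 0.02-0.03. A Jarlsberg patient who exits at week 16 has that reading copied to week 32. An exit at the patient's last visit leaves nothing to carry.

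With no mean BMD change and SD 0.09, LOCF puts the mean week-32 change 0.003-0.009 g/cm2 too low. In one scenario it is 0.0053 for the full sample and 0.0017 under LOCF: 0.0036 against a standard error of 0.0238 for 24 patients, or 0.15 standard errors.

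**The case against.** **The wording leans to 10.2.** The patients are called withdrawn, 10.2 is the withdrawal class, and its heading concerns the study question, which a T-score below the limit plainly is. It also takes reasons that only might be related. Vitamin D and calcium are trial treatment too (1.5), so bone loss in a control is hard to document as unrelated. This stands: 10.2 is the more natural reading. It is still only a reading, and the test written in both classes is relation to treatment.

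**10.1 does not say excluded.** Correct. It says replaced and separately described. Exclusion is inferred from the contrast with 10.2, so the losses above are conditional on it.

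**Both classes give a wrong result.** A reader might infer this. The documents do not support it: under 10.2 the week-16 value and the event are both intact.

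**The BMD change is biased upward because only completers are averaged.** This too might be inferred, but the plan prescribes no completer average. It names LOCF (10.2) and ANCOVA with repeated measurements (11.2).

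**The large figures need a doubtful SD.** This stands. The 14-25% requires 0.09 g/cm2 to be the SD of change.

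**A repeated-measures model is not automatically unbiased.** This stands. 5.1 scans several sites and does not say which T-score triggers exit. In a simulation with exit on one site and analysis of another (assumed correlation 0.6-1.0, SD of change 0.09), a regression on the analysed site alone was biased by +0.0025 to +0.007 g/cm2, while LOCF was near zero.

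**This could wait for the analysis plan.** Event dating and censoring could. Replacement, analysis-set membership and LOCF are already fixed in section X.

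**Conclusion.** The point holds in a limited form. The protocol removes patients on the value of its main variable and does not say which exit class applies. If they are treated as 10.1 drop-outs and left out, the week-16 difference shrinks by about 14-25% at an SD of change of 0.09 g/cm2 and by about 2-11% at 0.02-0.045. These figures rest on the assumed T-unit, baseline distribution and noise share. The second set of assumptions gives 14-27% at 0.09 and 2-6% at 0.02-0.03. The loss works against the cheese, and third-aim events may go with the patients.

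If they are treated as 10.2 withdrawals, the randomised comparison and the event are unaffected. The harm is confined to visits after exit, where LOCF fixes a control's on-cheese change at zero.

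The differing limits (-2.5 or lower in 1.8.2; strictly below -2.5 in 4.1, 6.2.2 and 6.2.3) are a separate contradiction in the definition of the same event.

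**What to change.** Leave the clinical withdrawal rule unchanged.

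1. In section X, state that exit on the T-score is an outcome event. The patient is never classed as a drop-out or replaced, stays in ITT and PP with the observed DXA in the week-16 comparison, and counts for the third aim in the randomised arm.
2. For visits after exit, do not use LOCF. Fit the repeated-measures model of 11.2 by likelihood to all observed values, including the site and T-score that triggered exit. The model relies on missing at random, which fails if exit is triggered by a site left out of it, so the protocol should name the triggering site.
3. Report T-score exits by arm beside the later BMD means.
4. Reconcile 1.8.2 with 4.1, 6.2.2 and 6.2.3 on the limit.

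The cost is a paragraph in section X and a sentence in 11.2, with no extra patients, visits or procedures. The downside is that later-visit estimates rest on a model and have slightly wider intervals.

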#### *6.2.3: Follow-up phase*

The patients allocated to Vitamin D + Ca at baseline will meet for a new investigation after 4 weeks which is week 20 in the study. Blood samples will be taken for measurements of Osteocalcin and the BTMs. Additionally, concomitant medication, AE and treatment compliance will be recorded. Cheese for the next 4 weeks will be delivered. A new delivery will be handed over by a representative from the Meddoc team every week. At every delivery the patients receive a new treatment & activity form and asked to perform daily registrations. The last visit in the follow-up part will be at week 32 for the patients randomized to OED of Jarlsberg cheese at baseline. The physical examination will be equal with the one previously performed. The patients must perform a new diet registration during the following 4 days and undergo the third DXA investigation for measurements of BMD. Additionally, the patients will record their change in concomitant medication. Blood samples will be collected for measurements of Osteocalcin, vitamin K2, BTMs, HbA1C, Lipids, Interleukins, cytokines, and other hematological and biochemical variables. Patients with a T-score < -2.5 based on the DXA investigation will be classified as Osteoporotic and withdrawn from the study. If possible and in accordance with the responsible investigator, the patient will be given Antiresorptive treatment together with OED of Jarlsberg cheese and vitamin D + Ca. The patients allocated to vitamin D + Ca only at baseline will meet for a new visit at week 32 and the last visit in the follow-up part at weeks 48. These investigations will be equal to those performed at week 16 and 32 for the Jarlsberg group.

#### *6.2.4: End of study*

The end of the study will be Week 32 for the patients allocated to Jarlsberg cheese at baseline and Week 48 for those allocated to vitamin D + Ca at baseline. At the end of the study, the “End-of-treatment” Case Record Form (CRF) must be filled in by the investigator.

#### *6.2.5: One year follow-up*

The patient finalizing the study will be asked if they want to continue with daily OED of Jarlsberg cheese. They will receive the cheese free of charge but must meet for a new investigation one year later. This investigation will consist of a physical examination, and a DXA measurement. A new blood sample will be taken for measurement of Osteocalcin, BTMs, vitamin K2, lipids and HbA1C. Additionally, the number of bone fractures during the last year will be recorded.

### 6.3: Treatment administration of the study

#### 6.3.1: Daily doses

All the patients will receive 20µg vitamin D and 1000 mg Calcium (Ca) tablets daily during the study. The daily Optimal Efficacy Dose (OED) of Jarlsberg differs between genders and menopausal stage. For fertile women the daily OED of Jarlsberg will be 57 g. For men passed the age of 50 years it is **XX** g and for post-menopausal women it is **YY** g.

**Tabell III: Cheese Energy Contents per 100 grams**

Energy Sources	Jarlsberg Cheese
Total Energy	1458 kJ (351 kcal)
fat	27g
carbohydrates	0 g
protein	27g
calcium	770mg
phosphate	550mg

#### 6.3.2: The supply of Cheese, vitamin D + Ca

The patient will receive the cheese and vitamin D + Ca at the visits every 8 weeks during the study. However, the patients needed new delivery every four weeks. These deliveries in between will be performed by a study nurse in the Meddoc team who brings the new delivery home to the patients and collecting the compliance & activity form.

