### 1.6.2 Randomization:

Patients included in the study will be allocated to one of the two treatment groups by block randomization with random block size between 2 and 6.

**1.7: Main variables:** The main response variable will be the change in Bone Mineral Density (BMD) and recorded at baseline and every 16 weeks. The second main variables will be total Osteocalcin (tOC), carboxylated osteocalcin (cOC), the osteocalcin ratio  $R_O$  defined as the ratio between cOC and under-carboxylated osteocalcin (ucOC) [ $R_O = cOC / ucOC$ ] and measured at start, week 4, week 16, week 20, week 32 and week 48. Additionally, the bone markers cross-linked C-telopeptide type I collagen (CTX), procollagen type 1 N-terminal propeptide (PINP), bone specific ALP (BALB) and Parathyroid hormone (PTH) will be measured at the same visits. At baseline and every 16 weeks, the following variables will be measured: Vitamin K2 and the different vitamers MK-7, MK-8, MK-9, and MK-9(4H) used as explanatory variable; Diet registration as controlling variables and HbA1C, Lipids, biochemical variables together with “Quality-of-Life” (QoL) questionnaire as supporting variables. The Interleukins IL-1 $\beta$ , IL6, IL8, IL10 and the Cytokines TNF- $\alpha$ , NF- $\kappa$ B (RANK-L), OPG and TGF- $\beta$  will be measured initially and at the last visit in the study. The Common Terminology Criteria for Adverse Events version 4.0 (CTCAE) will be used for registration of Adverse Events (AE) and toxicity score at every investigation visit.

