## 1.11: Flow chart

ITEMS	Screening & Baseline	Weeks					Follow-Up +1 Year
		Comparison 4	16(0)	20 (4)	Switch 32(16)	48(32)	
Inclusion and Exclusion criteria	x						
Oral & written informed consent	x						
Patient factors	x						
History of disease	x						
Diet registration	x		x		x	x	
Physical exam.	x		x		x	x	x
DXA-screening	x		x		x	x	x
Concomitant medication	x	x	x	x	x	x	x
Treatment compliance 		x	x	x	x	x	x
Blood sampling							
- Total Osteocalcin (tOC)	x	x	x	x	x	x	x
- Carboxylated Osteocalcin (cOC)	x	x	x	x	x	x	x
- Under carbox. Osteocalcin (ucOC)	x	x	x	x	x	x	x
- Collagen1 (CTX-1)	x	x	x	x	x	x	x
- Procollagen 1 (PINP)	x	x	x	x	x	x	x
- Bone specific ALP	x	x	x	x	x	x	x
- Parathyroid hormone (PTH)	x	x	x	x	x	x	x
- Vitamin K 1	x		x		x	x	
- MK-7	x		x		x	x	
- MK-8	x		x		x	x	
- MK-9	x		x		x	x	
- MK-9(4H)	x		x		x	x	
- Vitamin D	x		x		x	x	x
- Haemoglobin	x						
- Ferritin	x						
- Creatinine	x		x		x	x	
- HbA 1c	x		x		x	x	x
- Ca, Mg, Albumin	x		x		x	x	x
- Urea, Phosphate	x		x		x	x	x
- LDL-cholesterol	x		x		x	x	x
- HDL-cholesterol	x		x		x	x	x
- Interleukins /cytokines	x				x	x	
- TSH & FT4	x				x	x	
Adverse Events [CTCAE]	x	x	x	x	x	x	
End of treatment					x	x	

**Red numbers** indicate only the visits after switching to Jarlsberg in the control group.

 Treatment compliance will be performed every four weeks.

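### Adverse events and concomitant medication are recorded only at clinic visits 4, 12 and 16 weeks apart, although study staff already make four-weekly deliveries and collect a daily form

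*Protocol*

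**What the plan says.** **When AEs are recorded.** Section 1.7 says that CTCAE "will be used for registration of Adverse Events (AE) and toxicity score at every investigation visit". The AE row of the flow chart (1.11) marks baseline and weeks 4, 16, 20, 32 and 48, and nothing between them.

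**When patients are seen.** Section 1.8.2: "All the patients meet for new visits at week 4, week 16, and week 32". It adds: "Patients allocated to only vitamin D + Ca tablets at baseline well additionally meet for visits at week 20 and week 48". For week 4, section 6.2.2 says: "Additionally, concomitant medication, adverse events (AE) and treatment compliance will be recorded". For week 20 in the switched controls, section 6.2.3 says: "Additionally, concomitant medication, AE and treatment compliance will be recorded".

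**What happens between visits.** Section 1.8.2 gives all participants new supplies every four weeks. Section 6.2.2: "A new delivery will be handed over by a representative from the Meddoc team at week 8 and week 12 in the study". Section 6.3.2: "These deliveries in between will be performed by a study nurse in the Meddoc team who brings the new delivery home to the patients"; the same person collects the compliance & activity form. Section 5.7 limits that form to treatment intake and physical activity. A footnote to the flow chart says: "Treatment compliance will be performed every four weeks". No section has AEs or medicines asked about at a delivery.

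**Reporting by the patient.** Section 6.6 advises participants to contact the investigator about severe AEs, and also about other conditions that trouble them.

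**The concern.** The Protocol sets itself a demanding standard for AEs. Section 5.6.3 requires every AE to be described in detail, with its severity and its possible relation to treatment. Section 5.6.2 counts mild symptoms that need observation only as Grade 1, so minor complaints are in scope. The causality categories in the same section turn on the timing of the event relative to intake, so onset dates matter. Section 1.8.1 names CTCAE as the measure of tolerability and toxicity.

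A mild complaint or a short course of another medicine early in a 12- or 16-week gap may be forgotten by the next visit, or remembered without a usable date. What is at stake is the completeness of the tolerability record and the quality of the causality assessment. The BMD endpoint is not affected.

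**Working it through.** **Inputs.** Visits with AE recording, from sections 1.8.2, 6.2.2 to 6.2.4 and the flow chart:
- Jarlsberg group: weeks 0, 4, 16, 32.
- Initial control group: weeks 0, 4, 16, 20, 32, 48.

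**Step 1: recall windows.** Window = week of this visit minus week of the previous visit.

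| Group | Windows (weeks) | Total | In windows of 12 weeks or more |
|---|---|---|---|
| Jarlsberg | 4, 12, 16 | 32 | 12 + 16 = 28; 28/32 = 87.5% |
| Control | 4, 12, 4, 12, 16 | 48 | 12 + 12 + 16 = 40; 40/48 = 83.3% |

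**Step 2: randomised comparison, weeks 0 to 16.** Both groups have windows of 4 and 12 weeks. The week-16 assessment alone covers 12/16 = 75% of the period. The 16-week windows fall after week 16 in both groups.

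**Step 3: existing contacts between visits.** If deliveries are four-weekly throughout, those that do not coincide with a clinic visit are:
- Jarlsberg: weeks 8, 12, 20, 24, 28, which is 5.
- Control: weeks 8, 12, 24, 28, 36, 40, 44, which is 7.

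With AE entries collected at these contacts, every scheduled window becomes 4 weeks. The longest falls from 16 to 4, and within the randomised phase from 12 to 4.

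**Step 4: do the intervals agree across sections?** They do not.
- Section 6.3.2 speaks of visits every 8 weeks, and section 5.2 of bone-marker sampling every 8 weeks. No window in Step 1 is 8 weeks long.
- Section 6.2.3 speaks of weekly deliveries after week 20. Sections 1.8.2 and 6.3.2 speak of four-weekly ones.

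If visits with AE recording did take place every 8 weeks, the longest window would be 8 weeks, and the change would halve it rather than quarter it. The direction of the result does not depend on which statement is kept, but its size does.

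**The case against.** Several points on the other side have force.

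- **Early assessments.** A reader might infer that AEs are asked about only every 12 to 16 weeks. The documents do not support that. There is an assessment at week 4 for everyone and at week 20 for switched controls, in each case 4 weeks after the treatment starts. This stands; the long gaps come later.
- **Reporting between visits.** A reader might infer that section 6.6 covers serious events only. It does not: its wording extends to other troublesome conditions. This stands as well. But the route depends on the patient's initiative, and a complaint that seems too small for a call waits until the next visit. It also does not mention medicines.
- **No unequal schedule in the comparison.** Up to week 16 both groups are asked at the same times, so the schedule itself creates no difference between them. This stands. After week 16 the schedules differ.
- **Size.** One could assume a rate of forgetting and derive a percentage of lost events. The Protocol gives no such rate, and complaints that persist under daily intake would still be present at the visit. No percentage is claimed here.
- **Low stakes.** Tolerability is not among the aims (1.3, 2.4), section 8.1 describes a cheese on general sale with no known AEs except in milk intolerance, and milk allergy and gastrointestinal disorder are excluded (3.2.2). This limits the weight of the point. It does not set aside section 5.6.3, which asks for all AEs.
- **Prompting.** Section 4.1 calls the trial open (section 1.6.1 says single-blinded). A daily symptom line may draw more reports from patients who know that they eat the cheese. This is a genuine cost of the change.

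**Conclusion.** The point holds as a minor weakness in how AEs and concomitant medication are collected. Scheduled recording is tied to clinic visits with windows of 4, 12 and 16 weeks; 28 of 32 weeks (Jarlsberg) and 40 of 48 weeks (control) lie in windows of 12 weeks or more; and 12 of the 16 randomised weeks depend on one assessment. Reporting by patients between visits is possible but unsystematic, so mild events and onset dates may be missed.

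The documents do not show how many events would be lost, nor that the loss would favour one group. The window lengths rest on the visit schedule in section 1.8.2 and the flow chart, and the reduction to 4 weeks also rests on four-weekly deliveries. Sections 5.2, 6.2.3 and 6.3.2 contain statements that conflict with these.

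**What to change.** 1. Add two lines to the existing compliance & activity form: one for symptoms, and one for new or changed medicines with dates. Use the same wording in both groups.
2. In sections 6.2.2, 6.2.3 and 6.3.2 and in the flow chart, state that the person making each four-weekly delivery collects these entries and passes them to the investigator, who alone grades them by CTCAE. The role needs one name: section 6.3.2 has a study nurse, section 6.2.2 a team representative and section 6.2.1 one responsible person.
3. Reconcile the 8-weekly visits in section 6.3.2, the 8-weekly sampling in section 5.2 and the weekly deliveries in section 6.2.3 with the four-weekly deliveries and visit schedule in section 1.8.2 and the flow chart.

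**Cost.** No new visit and no new staff. With 30 patients per group (section 11.3) all completing, the contacts concerned number at most 30 × 5 + 30 × 7 = 360, each needing a few minutes, plus some extra eCRF entries and grading work. The AE count will be somewhat higher, and prompted reports in an open trial may be coloured by expectation. The report should therefore separate events first noted on the form from those recorded at visits.
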